11.2.4 Demographic and Baseline Characteristics

Descriptive statistics of demographic variables (sex, age, race/ethnicity) will be presented for all enrolled study subjects, and for subjects stratified by study site and by assigned study arm.

Continuous variables as a minimum will be described by number of non-missing observations (n), arithmetic mean, standard deviation (SD), minimum, median, and maximum. Categorical variables will be presented using the number of observations in each category, and corresponding proportions (expressed as percentages).

11.2.5 Analysis of Primary Endpoint

The null hypothesis to be tested is

$$H_0: D_A - D_{C/S} = 0,$$

where D_A is the change in pain score after an elapsed time of 2 hours using the active device, and $D_{C/S}$ is the change in pain score after an elapsed time of 2 hours using the control/sham device.

⁴ Van Buuren S and Goothius-Oudshoorn K. *mice*: Multivariate imputation by chained equations. *Journal of Statistical Science* 2011, 45: 1-67.

In order to assess whether there is a possible baseline effect, the mean baseline pain score (*i.e.* mean pain score at symptom onset) using the active device shall be statistically compared to the mean baseline pain score using the active/sham device, using a two-sample *t*-test at a significance level of $\alpha = 0.05$.

In order to assess whether there is a possible effect of rescue medications on the primary endpoint, the proportion of subjects using rescue medications within 2 hours of symptom onset will be statistically compared between the two study arms, using Fisher's exact test at a significance level of $\alpha = 0.05$.

If there is no significant difference in baseline pain scores and no significant difference in early use of rescue medications between the two device types, the null hypothesis will be tested using the difference between the change in pain scores after 2 hours using the active device and the change in pain scores after 2 hours using the control/sham device.

The distributions of these differences will be tested for normality using the Shapiro-Wilk test at a significance level of $\alpha = 0.05$. If the distributions are consistent with a hypothesis of normality, the above null hypothesis will be tested using a two-sample *t*-test; otherwise, the null hypothesis will be tested using a non-parametric Mann-Whitney test. The mean and associated 95% confidence interval for the true difference between the two devices will be computed, along with the *p*-value associated with the null hypothesis.

If there is a significant difference in baseline pain scores and/or early use of rescue medications between the two study arms, an analysis of covariance (ANCOVA) model shall be fitted to the data, relating the difference in pain scores after 2 hours to the device type (active vs. control/sham), while controlling for any significant covariates. A *p*-value associated with the test of the hypothesis of no effect of the active device on change in pain score after 2 hours will be computed.

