6.3 Pain Scale

Subjects will be asked to rate their headache pain using an 11-point scale, *i.e.* on an integer scale from 0 to 10 inclusive, with 0 indicating no pain and 10 indicating the worst pain imaginable. The scale can be interpreted clinically as follows:

- 10: worst pain imaginable;
- 8-9: very severe pain;
- 6-7: severe pain;
- 4-5: moderate pain;
- 1-3: mild pain;
- 0: no pain.

The 11-point pain scale has been validated for use in migraine headache evaluations.¹

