11.2 Proposed Analyses

A statistical analysis plan, containing detailed information regarding the proposed statistical analyses of study data, will be created and approved prior to database lock.

Unless otherwise stated, all statistical testing will be two-sided and will be performed using a significance level of $\alpha = 0.05$.

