11.2.3 Handling of Missing Data

In the intention-to-treat population, any missing pain scores at time points of 2 and 4 hours after application of the device shall be imputed using a multiple imputation procedure, with study arm, age, sex, baseline pain score, number of severe or very severe headaches experienced while enrolled in the study, and pain scores at 2 and 4 hours after application of the device for subsequent severe or very severe headaches experienced while enrolled in the study as predictors. Imputation procedures shall utilize predictive mean matching.⁴ A total of 50 sets of multiple imputations shall be generated; the analysis of the primary endpoint shall be conducted for each set, and a pooled estimate of the difference in mean improvement between the two devices will be computed, along with a 95% interval estimate and p -value associated with the null hypothesis.

In the per-protocol population, subjects with a missing value of an exploratory endpoint will not be included in the evaluable population for that endpoint.

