11.2.6 Analysis of Secondary Endpoint

In order to compare the mean change in pain score after an elapsed time of 4 hours using the active device to the mean change in pain score after an elapsed time of 4 hours using the control/sham device, the analyses as described in section 10.2.5 for the primary endpoint shall be followed.

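### The Mann-Whitney branch of the primary test (11.2.5) cannot be carried through the 50-set imputation (11.2.3) as written

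*Combined protocol and SAP*

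**What the plan says.** Section 11.2.1 places the primary and secondary endpoints in the intention-to-treat population, so the imputation in section 11.2.3 applies whenever a 2-hour or 4-hour score is missing. Section 11.2.3 generates 50 sets by predictive mean matching. It then states that "the analysis of the primary endpoint shall be conducted for each set, and a pooled estimate of the difference in mean improvement" is to be computed, "along with a 95% interval estimate and p -value associated with the null hypothesis". No pooling rule is named.

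Section 11.2.5 begins with two pre-tests: a t-test on baseline pain and Fisher's exact test on early rescue medication. If either is significant, the analysis is ANCOVA. If neither is, "The distributions of these differences will be tested for normality using the Shapiro-Wilk test" at the 0.05 level. Without rejection the test is a two-sample t-test; "otherwise, the null hypothesis will be tested using a non-parametric Mann-Whitney test". Whichever of the two tests is used, "The mean and associated 95% confidence interval for the true difference between the two devices will be computed".

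For 4 hours, section 11.2.6 says that "the analyses as described in section 10.2.5 for the primary endpoint shall be followed". There is no section 10.2.5; 11.2.5 is evidently meant. Section 11.2.3 imputes 4-hour scores but mentions only the primary endpoint when it describes pooling.

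**The concern.** Pooling over imputed sets needs an estimate and its standard error from each set. The t-test and the ANCOVA both supply them; Mann-Whitney does not. An analyst who reaches the Mann-Whitney branch with imputed data therefore has no instruction on three matters: whether the choice of test is made once or in each set, what to do if the 50 sets do not all choose the same test, and how rank tests are combined into one p-value.

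Two analysts could both follow the plan and report different primary p-values, with the choice made after the data are seen. Even with complete data, the Mann-Whitney branch puts a rank-test p-value beside a confidence interval for a mean difference, and the two need not agree at the 0.05 boundary.

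**Working it through.** **1. The plan's own sample size.** Section 11.1 gives a difference of 4 - 2 = 2 points, SD 2.0, alpha 0.05 (two-sided, section 11.2) and 27 per arm. For a two-sample t-test, df = 2 × 27 - 2 = 52 and the noncentrality is (2/2) × √(27/2) = 3.67, so power is 95.0%. For dropout, 27/0.8 = 33.75, so 34 per arm and 68 in total. The figures reproduce, and they rest on a t-test.

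**2. What pooling requires.** Let Q be the mean difference in one set and U its squared standard error. Rubin's rules give the average of the 50 Q values as the estimate, with variance T = (average U) + (1 + 1/50) × B, where B is the variance of Q across sets. One t statistic, estimate/√T, then gives the interval and the p-value. Mann-Whitney returns a rank statistic and a p-value, with no Q or U on the scale of mean improvement that section 11.2.3 pools.

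**3. When the problem arises.** Three conditions must hold together: at least one 2-hour score is missing, both pre-tests are non-significant, and Shapiro-Wilk rejects. With complete data, only the pairing of a rank p-value with a mean-based interval remains.

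**4. How often Shapiro-Wilk would reject.** Scores are recorded "on an integer scale from 0 to 10 inclusive" and baseline must be 6 or more, so change scores are discrete and bounded. The documents give no score distribution, so this was simulated (20,000 trials per cell). Assumptions: three baseline mixes over 6-10; sham improvement 2 points; active improvement 2 points plus an effect of 0, 1 or 2; normal error with SD 2; 2-hour score tracking baseline; rounding and clipping to 0-10.

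| Shapiro-Wilk applied to | 27 per arm | 34 per arm |
|---|---|---|
| each arm (rejects in at least one) | 33-44% | 39-55% |
| residuals pooled over arms | 16-23% | 21-31% |

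The plural wording in section 11.2.5 favours the first row.

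**5. Choosing the test once or per set.** A small simulation used 34 per arm, 50 predictive-mean-matching sets using arm and baseline only, about 150 trials per scenario, and effects of 0, 1 and 2 points. The missing rate was assumed. Monte Carlo error is up to about 4 points.

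| Missing 2-hour scores | Trials in which the 50 sets split between t-test and Mann-Whitney |
|---|---|
| 5% | 39-48% |
| 10% | 60-78% |
| 20% | about 83% |

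The 50 Mann-Whitney p-values fell on both sides of 0.05 in 9-65% of trials.

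**6. What it changes.**

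- Type I error with the gate: 4.7-5.3%.
- Power at 27 per arm, 2 points: 94.0-94.8% if the t-test is always used, 93.8-94.7% with the gate. These lie slightly below 95.0% partly because, when scores track baseline, clipping cuts the true difference to about 1.91-1.93.
- Complete data, t-test and Mann-Whitney verdicts differ: about 0.3-1% of trials at 2 points, 2-4% at 1 point.
- Imputed data at 34 per arm, 5-20% missing, pooled mean difference against a pooled rank z, counted only where Shapiro-Wilk (applied once, to observed scores) selects Mann-Whitney: 0-0.7% at 2 points, 0.9-2.8% at 1 point (1,200 trials per cell).
- Pooled mean difference against the median Mann-Whitney p-value, counted over all trials of the small simulation in step 5: 1-2% at 2 points, 5-8% at 1 point.

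**7. Power of a baseline-adjusted model** at 27 per arm, 2 points: 93.9-94.3% if the 2-hour score tracks baseline one-for-one (t-test 94.5%), and 98.9-99.4% if it does not track baseline at all (t-test 94.0-94.8%). With half tracking the gain over the t-test is 1-2 points.

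**The case against.** A reader might infer that the protocol names two contradictory primary tests. The text does not go that far. Section 11.2.3 runs the primary analysis within each set, which places 11.2.5 and all its branches inside the imputation. Both sections speak of a p-value for the null hypothesis, and neither says that the pooled mean difference must supply it. A consistent reading exists: run whichever test applies in each set, combine the p-values, and pool the mean difference as the estimate only. That reading still needs a combining rule and a rule for mixed branches, and the plan has neither.

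A reader might also infer an inflated error rate or an underpowered trial. Step 6 supports neither.

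Nor is the 20% dropout allowance in section 11.1 a rate of missing scores. Subjects without a qualifying headache are left out of the population (sections 6.4 and 11.2.1), not imputed. The missing-score rates used above are therefore assumptions.

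Finally, section 11.2 promises an SAP "containing detailed information regarding the proposed statistical analyses of study data, will be created and approved prior to database lock", and combining rules can properly be set there. This objection stands in part. The SAP could make the step executable, but rules for combining rank tests would still leave a rank p-value beside a mean-based interval, because 11.2.5 itself asks for that pairing. It is also fair to say that the gap alone does not require a baseline-adjusted model; that model is recommended on its merits.

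**Conclusion.** The point holds as an incompatible and incompletely specified step. The Mann-Whitney branch supplies nothing that section 11.2.3 can pool, and the branch and combining rules are absent. The branch is likely to be reached often, but changing the test seldom changes the conclusion: at the planned 2-point effect, verdicts differ in at most about 2% of trials under any comparison tried. The larger figures, up to 8%, come from a 1-point effect and a small simulation. All rates rest on assumed score distributions and assumed missingness, and the rescue-medication pre-test was not simulated. The case for changing the text is one coherent estimate, interval and p-value, with no choice left until after the data are seen. Severity is minor to should-fix.

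**What to change.** - Delete the Shapiro-Wilk gate in section 11.2.5 and, through 11.2.6, for the 4-hour endpoint.
- In every imputed set, fit one pre-specified linear model of change in pain score on device and baseline pain score. This replaces the conditional baseline test.
- Pool the device estimate and its standard error by Rubin's rules, so that one mean difference supplies the estimate, 95% interval and p-value. State that this applies at both 2 and 4 hours, and correct the cross-reference in 11.2.6.
- Keep Mann-Whitney on observed data as a sensitivity analysis.
- State how the rescue-medication rule in 11.2.5 relates to this model.

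A smaller change would put the two-sample t-test where the gate now stands, pool it in the same way, and leave the baseline rule as it is.

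**Cost.** Sample size and data collection do not change, because baseline pain is already recorded. The analysis would rely on approximate normality of means at 27-34 per arm, which the rank-based sensitivity analysis checks. The model uses one further degree of freedom: about half a point of power if the 2-hour score tracks baseline one-for-one, with a gain of 1-2 points at half tracking and 4-5 points at none. Changing 11.2.5 is a protocol amendment under section 10.2. It needs written agreement between investigator and sponsor, with IRB/EC approval if it materially alters the design, or submission for information if it is administrative. The pooling detail can go in the SAP before database lock.

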4.1 Primary Endpoint

The primary endpoint variable is the change in migraine pain as measured on an eleven-point pain scale, defined as the pain score after an elapsed time of 2 hours following application of the device minus the pain score at onset of migraine symptoms, with respect to the first severe or very severe migraine headache (defined as a pain score of 6 or greater at onset of migraine symptoms) experienced by an enrolled subject.

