4.3 Exploratory Endpoints

Exploratory endpoint variables are:

- The proportion of subjects who report mild or no symptoms (defined as a pain score of 3 or less) after an elapsed time of 2 hours following application of the device, with respect to their first severe or very severe migraine headache;
- The proportion of subjects who require abortive medication to control their first severe or very severe migraine headache within 8 hours following application of the device; and
- The proportion of subjects who report sensitivity to light after elapsed times of 2 hours and 4 hours following application of the device, with respect to their first severe or very severe migraine headache.

5. Inclusion/Exclusion Criteria

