6.4 Procedures and Assessments

Subjects will be directed to:

- apply the study glasses at the first onset of aura, or as soon as possible once they experience symptoms consistent with the onset of a migraine attack.
- avoid taking abortive medication for the first four hours of a migraine attack. If abortive medications cannot be avoided, the subject should document use.
- record the following information for the first (and all subsequent) severe or very severe migraine headaches that they experience while enrolled in the study:
 - The date and time of symptom onset;

¹ Kwong WJ and Pathak DS. Validation of the eleven-point pain scale in the measurement of migraine headache pain. *Cephalgia* 2007; 27: 336-342.

- The pain score (as assessed on the 11-point pain scale) just prior to the application of the study glasses (score needs to be greater than or equal to 6 to qualify as a severe or very severe headache);
- The time at which the study glasses are applied;
- Whether the subject was wearing prescription eyewear in addition to the study glasses, or whether the study glasses alone were worn;
- The pain score (as assessed on the eleven-point pain scale) 2 hours after the study glasses are applied;
- The pain score (as assessed on the eleven-point pain scale) 4 hours after the study glasses are applied;
- The type of abortive medication taken (if any) to control headache symptoms, the dosage taken, and the time at which the medication is taken; and
- Any experience of light sensitivity within 4 hours after the study glasses are applied, and the time at which light sensitivity is first experienced.

Subjects will participate in the study for a maximum of four (4) weeks \pm 3 days after enrollment; if a given subject does not experience a severe or very severe migraine headache within four (4) weeks, that subject will not be included in the evaluable study population.

Study coordinators will contact subjects once per week to ensure they are wearing the study device as instructed, and that they are recording the requested information related to their headaches. These weekly contacts will also enable coordinators to identify and address any barriers to adherence with the protocol.

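### Between-arm significance tests choose the primary model, so baseline adjustment is left to chance and early rescue use, a post-randomisation event on a different clock, can become a covariate

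*Combined protocol and SAP*

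**What the plan says.** Section 11.2.5 sets two preliminary tests at the 5% level. A t-test compares baseline pain between arms. Fisher's exact test is the second: "the proportion of subjects using rescue medications within 2 hours of symptom onset will be statistically compared between the two study arms". If neither is significant, the comparison is unadjusted. A Shapiro-Wilk test then picks the t-test where normality is not rejected; "otherwise, the null hypothesis will be tested using a non-parametric Mann-Whitney test". A mean difference with a 95% confidence interval is requested in this branch. The other branch begins "If there is a significant difference in baseline pain scores and/or early use of rescue medications between the two study arms" and fits an ANCOVA "while controlling for any significant covariates". No covariate is fixed in advance.

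Section 11.2.6 applies the same rule at 4 hours (it cites 10.2.5, evidently meaning 11.2.5) and does not say whether the rescue window changes.

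Four other places bear on this:
- Section 4.1 defines the endpoint as "the pain score after an elapsed time of 2 hours following application of the device minus the pain score at onset of migraine symptoms".
- Section 4.3 has as an exploratory endpoint the share of participants "who require abortive medication to control their first severe or very severe migraine headache within 8 hours following application of the device".
- Section 6.4 asks subjects to "avoid taking abortive medication for the first four hours of a migraine attack", with any use documented. It records onset, application and medication times, and takes the first pain score "just prior to the application of the study glasses".
- Section 11.2.7 stratifies the responder analysis by baseline pain with no preliminary test.

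**The concern.** Four features of the rule need attention.

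1. **Baseline gate.** The value of adjusting for baseline pain depends on how well it predicts the outcome, not on whether the arms happen to differ. The score is taken before the glasses go on. If arm affects neither that score nor who reaches a qualifying attack, the gate opens in about 5% of trials whatever the prognostic value of baseline.
2. **Rescue gate.** Rescue use arises after randomisation and may be a consequence of the device. The gate opens mainly when the device changes rescue, and adjustment then no longer estimates the overall device effect. The covariate wording is also ambiguous. It could mean variables that differ between arms or variables significant in the outcome model. If only the rescue gate opens, it is unclear whether baseline enters.
3. **Clock.** A check timed from onset misses rescue taken late in the endpoint window and counts rescue taken before the glasses go on.
4. **Test switch (minor).** A Mann-Whitney p-value does not test the mean difference reported beside it. Section 11.2.3 gives no rule for pooling that p-value over 50 imputed sets, and the Shapiro-Wilk choice can differ between sets.

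At stake are some power and a headline estimate whose meaning is fixed before data are seen.

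**Working it through.** **Plan's own figure.** Section 11.1 gives a 2-point difference, SD 2.0 and two-sided 5%. The normal formula is n = 2(1.960 + 1.645)² × 2.0² / 2² = 26 per arm. The noncentral t gives 94.2% power at 26 and 95.0% at 27, so 27 is right for an unadjusted t-test. Dropout: 27 / 0.8 = 33.75, hence 34. Both figures reproduce.

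**Baseline gate alone.** Assumed: baseline scores 6 to 10 with SD 1.195, and slope b of 2-hour pain on baseline. Change regresses on baseline with slope b − 1, so ρ² = (b − 1)² × 1.195² / 2.0². Always adjusting multiplies the variance by (1 − ρ²) × 1.022, where 1.022 is the simulated cost of the extra term. At b = 0.5: ρ² = 0.25 × 1.428 / 4 = 0.089, and 0.911 × 1.022 = 0.931, a change of −6.9%. Simulation used 27 per arm and 40,000 trials per slope:

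| Slope b | Variance change | Power, always adjusted | Power, gated | Type I, gated |
|---|---|---|---|---|
| 0 | −34.3% | 99.3% | 95.7% | 3.9% |
| 0.25 | −18.3% | 97.9% | 95.4% | 4.4% |
| 0.5 | −6.9% | 96.2% | 95.1% | 4.6% |
| 0.75 | −0.1% | 95.0% | 94.9% | 4.8% |
| 1 | +2.2% | 94.6% | 94.8% | 4.9% |

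The loss is about 0 to 2.5 points for slopes of 0.25 or more, and 3.6 at the extreme slope of 0.

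**How often the rescue gate opens.** Exact Fisher probabilities at 27 per arm, with assumed rates (active v sham): 1.9% at 20 v 20%, 1.35% at 5 v 10%, 11.6% at 22 v 35%, 31% at 10 v 30%.

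**Power and type I error of the full rule.** Assumed: slope 0.5, one logistic link from 2-hour pain to rescue common to both arms (log-odds 1 to 2 per SD), no rescue effect on the score, and ANCOVA covariates being those that differ between arms. At slope 0.5 the 2-hour SD is about 2, so the planned effect is about 1 SD. Sham rescue of 30 / 40% then implies active rescue of about 15 / 22% at log-odds 1 and 10 / 16% at log-odds 2.

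| Sham rescue | Power, plan |
|---|---|
| 20% | 93-94% |
| 31% | 90-93% |
| 40% | 87-93% |

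The comparators are 94-95% (unadjusted) and 95-97% (ANCOVA always adjusted for baseline). With no device effect, type I error of the plan is 4.2-4.8%.

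**What rescue adjustment estimates.** Assumed: a 2-point direct effect. If rescue does not lower pain but is strongly driven by it (20 v 43% use), the overall difference is 2.00 and the rescue-adjusted estimate 1.75. If rescue lowers pain by 2 points and is unrelated to pain (13 v 40% use), they are 1.45 and 1.99. The shift runs from −0.25 to +0.54.

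Averaged over all trials at 22 v 35%, where the gate seldom opens, the plan's mean estimate is 1.94 / 1.85 / 1.76 / 1.66 when rescue lowers pain by 0 / 1 / 2 / 3 points. The difference regardless of rescue is 2 − k × 0.13 for k points, which is 2.00 / 1.87 / 1.74 / 1.61. The sign turns between 1 and 2 points.

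**Clock.** With application d hours after onset, the last d/2 of the 2-hour window is unchecked: 12.5 / 25 / 50% for 15 / 30 / 60 minutes (assumed).

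**Test switch.** With 1 / 3 / 5 of 27 scores missing per arm, the 50 sets disagreed on Shapiro-Wilk in 33 / 76 / 83% of simulated trials. The imputation used arm and baseline only. Section 11.2.3 has more predictors, so this shows that disagreement can occur, not its rate.

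**The case against.** A reader might infer that the rule inflates type I error. The documents do not support that. The baseline gate alone is slightly conservative. For the rescue gate, if pain drives rescue in the same way in both arms and pain does not differ, rescue rates do not differ either. Inflation needs the device to change rescue by a route other than pain. The documents describe none, and subjects are blinded (Section 6.2). With unequal rates imposed anyway, type I error was about 6-8% at 8 v 31% and 8-15% at 10 v 40%. Those pairs are extreme, and the figures depend on the model.

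A reader might also infer that baseline gating changes the target. Under randomisation and a linear model, the raw and baseline-adjusted analyses estimate the same mean difference; only precision differs. Nor is the mean difference missing after the Mann-Whitney choice, since Section 11.2.5 asks for it.

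Three further points carry weight. Subjects are asked to avoid abortive medication for four hours, so early use may be low and the gate seldom open. Glasses are to go on as early as possible, so the clock gap may be short. Section 11.2 promises a detailed SAP before database lock, which could define the covariates and the 4-hour window.

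These limit the size of the problem. They do not remove it, because the gates are already protocol text and nothing elsewhere overrides them.

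**Conclusion.** The point holds and should be corrected. The baseline gate gives up roughly 0 to 3 power points at the planned effect, depending on an assumed slope, with no bias in the target and no type I inflation. The rescue gate is the more serious part: it lets the data decide whether the headline estimate is conditional on a post-randomisation event, with a shift whose direction depends on how much rescue lowers pain. Under a common pain-rescue link, its power cost runs from about one point at 20% sham rescue to about seven at 40% with the stronger link, and is negligible if early rescue is rare. The clock mismatch is certain in the text but of unknown size. The test switch is minor.

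The sample size of 27 per arm is correct and stays sufficient. Confidence is high on the text and moderate on the magnitudes, because rescue rates, the pain-rescue link, the rescue effect, the slope, the baseline SD and the application delay are all assumptions.

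**What to change.** In Sections 11.2.5 and 11.2.6:
- Prespecify one ANCOVA of change in pain on assigned arm, with baseline pain always included, fitted in each imputed set and pooled. State that scores are used regardless of rescue use.
- Delete the baseline t-test and Fisher's test as gates, and do not use rescue as a covariate.
- Count rescue from device application to the 2-hour score (4-hour score for the secondary endpoint) and report it by arm, using times already recorded.
- Add one prespecified sensitivity analysis for scores recorded after rescue, run whatever the rescue comparison shows.
- Keep Mann-Whitney or a rank-based ANCOVA as a sensitivity analysis in place of the Shapiro-Wilk switch.
- Reconcile the baseline definition: at onset in Sections 4.1 and 11.2.5, before application in Section 6.4.

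The cost is wording, with no new data. One degree of freedom is spent (about 2% variance if the slope is 1), and the estimate includes any effect of rescue. If rescue strongly lowers pain and differs much between arms, the fix can have less power than the plan. In one assumed setting (8 v 31%, rescue lowering pain by 3 points) it was 70 v 77%, because the difference regardless of rescue is then 2 − 3 × 0.23 = 1.31 points.
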